6.1.3.6 Extent of exposure

Data rules for derivation of the start and stop dates of study drug administration are described in Section 4.7. Periods of backup contraception use will not be subtracted from the exposure time, unless stated otherwise (refer to Section 6.2.1).

The exposure with extension treatment (i.e. number of woman-years) will be analyzed descriptively, overall, by parity and by age, BMI, race, ethnicity and indication for Mirena use.

Completion status (introduced post-hoc after Year 6 database lock, prior to Year 7 database lock):

In order to show the number of “completers”, the completion status of the Month 12 visit (after Year 6 database lock) will be summarized.

Similar analyses will be performed after Year 7 and Year 8 database lock, showing the completion status of the Month 24 and Month 36 visit (after Year 7 and 8 database lock), respectively.

6.2 Efficacy

The primary analysis set will be the PAS Year 6 (for the analysis after Year 6), the PAS Year 7 (for the analysis after Year 7) and the PAS Year 8 (for the final analysis after 8 years), respectively, unless stated otherwise. Analyses will be repeated for the FAS.

6.2.1 Primary efficacy variable

The primary efficacy variable is the occurrence of pregnancy within years 6 through 8 of Mirena use (i.e. ‘3-year PI’, as defined below). However, for the analysis after 6 years of Mirena use, the primary efficacy variable is the occurrence of pregnancy within year 6 of Mirena use (i.e. ‘1-year PI’, as defined below), and for the analysis after Year 7, the primary efficacy variable is the occurrence of pregnancy within years 6 through 7 of Mirena use (i.e. ‘2-year PI’, as defined below).

The PI is defined as the number of pregnancies per 100 woman-years. The Pearl Index will be analyzed for the ‘extension treatment period’ starting at Day 1 of Year 6 of Mirena use. That means, for subjects who had her baseline visit prior to Day 1 Year 6, exposure and pregnancies between the baseline visit and Day 1 Year 6 will be excluded; for subjects who had their baseline visit after Day 1 Year 6, exposure and pregnancies between Day 1 Year 6 and baseline visit will be included. The following PIs will be calculated:

- ‘1-year PI (sixth year)’, PI obtained in the sixth year of treatment, i.e., number of pregnancies that occurred during the sixth year of treatment divided by time the women were at risk of getting pregnant in the sixth year of treatment.
- ‘2-year PI (sixth & seventh year)’, PI obtained in the sixth and seventh year of treatment, i.e., number of pregnancies that occurred during the sixth and seventh year of treatment divided by time the women were at risk of getting pregnant in the sixth and seventh year of treatment.
- ‘3-year PI (sixth, seventh & eighth year)’, PI obtained in the sixth, seventh and eighth year of treatment, i.e., number of pregnancies that occurred during the sixth, seventh and eighth year of treatment divided by time the women were at risk of getting pregnant in the sixth, seventh and eighth year of treatment.

Furthermore, the following PI will be analyzed for the entire study period starting at baseline visit, i.e., exposure and pregnancies between the baseline visit and Day 1 of Year 6 of Mirena use will be included:

- ‘Overall PI’, PI obtained during the whole study, i.e., number of pregnancies that occurred during the entire study period starting at baseline visit divided by the time the women were under a risk of getting pregnant.

The exact rules regarding how the crude exposure time will be calculated are given in Integrated Protocol Section 10.3.2.1 and Integrated Protocol Table 10–1 as well as in [Table 6–1](#) below.

Table 6–1: Definition of crude exposure times

PI	Reason for end of study/ continuation status	Crude exposure time
1-year PI (6th year)	Total expulsion	Date, when expulsion was discovered – Date of Day 1 Year 6 +1
	Partial Expulsion/ Mirena removal	Date of Mirena removal – Date of Day 1 Year 6 +1
	Pregnancy	Date of conception – Date of Day 1 Year 6 +1
	Lost to Follow-up	Maximum of (Date Mirena last known in situ – Date of Day 1 Year 6 +1; 1 day)
	Continues into 7th year of treatment	365 days
2-year PI (6th and 7th year)	Total expulsion	Date, when expulsion was discovered – Date of Day 1 Year 6 +1
	Partial Expulsion/ Mirena removal	Date of Mirena removal – Date of Day 1 Year 6 +1
	Pregnancy	Date of conception – Date of Day 1 Year 6 +1
	Lost to Follow-up	Maximum of (Date Mirena last known in situ – Date of Day 1 Year 6 +1; 1 day)
	Continues into 8th year of treatment	730 days
3-year PI (6th, 7th and 8th year)	Total expulsion	Date, when expulsion was discovered – Date of Day 1 Year 6 +1
	Partial Expulsion/ Mirena removal	Date of Mirena removal – Date of Day 1 Year 6 +1
	Pregnancy	Date of conception – Date of Day 1 Year 6 +1
	Lost to Follow-up	Maximum of (Date Mirena last known in situ – Date of Day 1 Year 6 +1; 1 day)
	Continues into 9th year of treatment	Minimum of (1095 days; Date of EOT visit – Date of Day 1 Year 6 +1)
Overall PI	Total expulsion	Date, when expulsion was discovered – Baseline visit date +1
	Partial Expulsion/ Mirena removal	Date of Mirena removal – Baseline visit date +1
	Pregnancy	Date of conception – Baseline visit date +1
	Lost to Follow-up	Maximum of (Date Mirena last known in situ – Baseline visit date +1; 1 day)
	Continued until EOT	Date of EOT visit – Baseline visit date +1

PI=Pearl Index; EOT=End of treatment

A pregnancy will be allocated to the time period(s) that are relevant for the calculation of the PIs described above, e.g., a pregnancy that occurs on day 400 will be relevant for the 7th year PI, the 2-year PI (6th & 7th year), the 3-year PI (6th, 7th & 8th year), and the overall PI. Pregnancies that occur before Day 1 Year 6 of Mirena use will not count for the 1-year PI, 2-year PI and 3-year PI. Pregnancies that occur after the Mirena was removed or an expulsion was discovered will not count for any PI calculation.

It should be noted that pregnancies that occur within 7 days after the end of exposure will count for the PI calculations.

Furthermore, it should be noted that pregnancies that occur after partial expulsion or first occurrence of non-compliance but before Mirena removal will count for the PI calculations.

Exposure times to be subtracted for Pearl index analyses:

Subjects who apply backup contraception are not at risk or are at lower risk of getting pregnant than subjects who do not apply backup contraception. In case a subject uses backup contraception (e.g., condoms to prevent sexually transmitted disease), the respective 28-day reference period(s) of backup contraception use will be excluded from the exposure time, unless a pregnancy occurred in that 28-day reference period. In the Pearl index analyses, the first 28-day reference period will start at Day 1 Year 6. Missing data will be considered as no use of backup contraception.

Primary analysis:

The primary method for the evaluation of the occurrence of pregnancy is the PI defined as the number of pregnancies per 100 woman-years.

The PIs and the corresponding 2-sided 95% confidence interval (CI) will be calculated using the model specified below.

Mathematical model for the calculation of the PI:

By assuming that the number of pregnancies follows a Poisson-distribution, the point estimate and the 95% CI for the PI can be calculated as follows:

$$PI = x/E,$$

$$\text{lower 95\% confidence limit of PI} = 0.5 \times \chi^2_{(0.025, 2x)} / E$$

$$\text{upper 95\% confidence limit of PI} = 0.5 \times \chi^2_{(0.975, 2(x+1))} / E$$

where x = number of pregnancies,

E = exposure in 100 woman-years,

$\chi^2_{(\alpha, df)}$ is the alpha-quantile from χ^2 -distribution with df degrees of freedom.

All PIs described above will also be presented by parity (no births vs. at least one birth), BMI (<30 kg/m² vs. ≥30 kg/m²) and age at insertion (<18 years vs. 18-25 years vs. 26-35 years, and <18 years vs. 18-35 years), age at baseline (18-25 years vs. 26-35 years vs. >35 years, and 18-35 years vs. >35 years), race and ethnicity. The age at insertion will be calculated as: age at baseline (recorded on the eCRF at baseline, Visit 2) minus 5 years.

To assess pregnancies with regard to subgroup combinations, e.g. by age and parity, a listing on all pregnancies providing detailed information regarding subject number, age, parity, date of Mirena insertion, date of baseline visit, date of Day 1 Year 6 of Mirena use, date of Mirena removal, (estimated) date of (partial/total) expulsion, estimated date of conception, location of pregnancy implantation at time of diagnosis, and estimated date of conception relative to Mirena insertion/ relative to Day 1 Year 6 of Mirena use/ relative to stop date of study drug administration will be provided.

Secondary analysis:

In order to fulfill the European guideline EMEA-‘Guideline on clinical investigation of steroid contraceptives in women’ (EMEA/CPMP/EWP/519/ Rev1, July 2005.) (2), the cumulative failure rate, i.e. the probability of getting pregnant will be calculated using the Kaplan-Meier method in addition to calculation of the different PIs.

Periods of backup contraception use will not be subtracted from the exposure time.

Sensitivity analysis:

The usual assumption for the calculation of the PI is a constant hazard for the event of becoming pregnant over time. As this cannot necessarily be assumed for the study treatment of this study, PIs will be calculated *per year*, as sensitivity analyses.

Similar analyses (PIs and cumulative failure rates) will be provided for ectopic pregnancies.

Sensitivity analysis (introduced post-hoc after Year 6 database lock, prior to Year 7 database lock):

The primary analysis (‘1 year PI (sixth year)’ after Year 6 database lock based on the PAS Year 6) was conducted using the following rules:

- 1 WY = 365 days
- Complete and incomplete 28-day cycles are used for the exposure calculation (i.e., the days of the last 28-day cycle are used even if incomplete)

A sensitivity analysis will be conducted using the following rules

- 1 WY = 13 28-day cycles (i.e., 364 days)
- Only complete 28-day cycles are used

Similar analyses will be performed after Year 7 and Year 8 database lock, i.e. ‘2 year PI (sixth and seventh year)’ after Year 7 database lock based on the PAS Year 7 and ‘3 year PI (sixth, seventh and eighth year)’ after Year 8 database lock based on the PAS Year 8, respectively. PIs will be also be calculated *per year*, i.e. ‘Year 6 PI’ and ‘Year 7 PI’ after Year 7 database lock based on the PAS Year 7 and ‘Year 6 PI’, ‘Year 7 PI’ and ‘Year 8 PI’ after Year 8 database lock based on the PAS Year 8.

As for the primary analysis, pregnancies that occur within 7 days after the end of exposure as well as pregnancies that occur after partial expulsion or first occurrence of non-compliance

but before Mirena removal will count for the PI calculations; 28-day reference period(s) of backup contraception use will be excluded from the exposure time.

Repeated analysis of the primary efficacy variable (introduced prior to Year 8 database lock) for the PAS Year 6 and PAS Year 7 based on the final database after Year 8:

For the analysis after 6 years of Mirena use, the primary efficacy variable was the occurrence of pregnancy within year 6 of Mirena use (i.e. ‘1-year PI’) based on the PAS Year 6, which was analysed based on the interim database after Year 6 and reported in the Year 6 CSR.

For the analysis after 7 years of Mirena use, the primary efficacy variable was the occurrence of pregnancy within years 6 through 7 of Mirena use (i.e. ‘2-year PI’) based on the PAS Year 7, which was analysed based on the interim database after Year 7 and reported in the Year 7 CSR.

These analyses (and the corresponding sensitivity analyses) will be repeated after the final database lock, to provide these results based on the most accurate and complete datasource, i.e. the final database after Year 8:

- For the PAS Year 6, based on the final database after Year 8:
 - ‘1-year PI’ (Year 6)
 - ‘1-year PI’ (Year 6) – based on only complete 28-day cycles
 - ‘1-year PI’ (Year 6) – for ectopic pregnancies
 - ‘1-year probability of getting pregnant’ (Year 6)
 - ‘1-year probability of getting pregnant’ (Year 6) – for ectopic pregnancies
- For the PAS Year 7, based on the final database after Year 8:
 - ‘2-year PI’ (Years 6 and 7) and PIs calculated *per year*, i.e. ‘Year 6 PI’ and ‘Year 7 PI’
 - ‘2-year PI’ (Years 6 and 7) and PIs calculated *per year*, i.e. ‘Year 6 PI’ and ‘Year 7 PI’ – based on only complete 28-day cycles
 - ‘2-year PI’ (Years 6 and 7) and PIs calculated *per year*, i.e. ‘Year 6 PI’ and ‘Year 7 PI’ – for ectopic pregnancies
 - ‘2-year probability of getting pregnant’ (Years 6 and 7) and probabilities calculated *per year*, i.e. ‘Year 6 probability of getting pregnant’ and ‘Year 7 probability of getting pregnant’
 - ‘2-year probability of getting pregnant’ (Years 6 and 7) and probabilities calculated *per year*, i.e. ‘Year 6 probability of getting pregnant’ and ‘Year 7 probability of getting pregnant’ – for ectopic pregnancies

Please note that due to a more accurate and complete exposure in the final database after Year 8 caused by the fact that the study is no longer ongoing but all subjects have completed the study (or discontinued prematurely), minor changes in these PIs and probabilities of getting pregnant (compared to the Year 6 CSR and Year 7 CSR, respectively) are expected.

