6.1 Inclusion criteria

1. Signed and dated informed consent
2. Women, 18 to 35 years of age at the time of screening (visit 1) who are currently using Mirena for contraception or for contraception and heavy menstrual bleeding. The duration of use of the current Mirena has to be at least 4 years 6 months at the start of screening phase but not more than 5 years at visit 2 and the woman is willing to continue with its use and has a continuing need for contraception.
3. Normal or clinically insignificant cervical smear not requiring further follow up (a cervical smear has to be taken at screening visit or a normal result has to be documented within the previous 6 months). Human papilloma virus (HPV) testing in subjects with atypical squamous cells of undetermined significance (ASCUS) can be used as an adjunctive test. Subjects with ASCUS can be included provided they are negative for high-risk HPV strains.

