9.6.3.4 Pregnancy test

A urine pregnancy test (urine hCG) will be performed at every visit as presented in Table 9–1. In case of a suspected pregnancy at screening or baseline visits, the subject must be withdrawn from the study and is considered a screening failure. If a pregnancy occurs during the study treatment period (i.e. after the baseline visit), subjects should immediately contact the investigator for an unscheduled visit (for reporting of pregnancies, see also Section 9.4.1). During the course of the study, additional urine hCG testing should be performed if there is clinical suspicion of pregnancy at any time.

In addition to the urine hCG tests performed by the site at each study visit, subjects will be provided with home urine pregnancy tests to be used whenever a pregnancy might be suspected.

If results of a home pregnancy test are positive or if a subject is unsure whether she is pregnant after performing the test, she should immediately contact the study site to schedule a visit and have a confirmatory test performed.

In the event of a positive urine hCG result, pregnancy should be confirmed according to the local standard of care (e.g., serum hCG testing).

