5.1 Assignment of analysis sets

Final decisions regarding the assignment of subjects to analysis sets will be made during the review of study data and documented (see Section 4.8).

The following statistical analysis sets will be defined:

Full analysis set (FAS):

All women who completed the baseline visit of the study

Primary analysis set Year 6 (PAS Year 6):

All women in the FAS with an age of 35 years or younger at baseline visit (i.e., an age of 36 or younger at end of Year 6)

Primary analysis set Year 7 (PAS Year 7):

All women in the FAS with an age of 34 years or younger at baseline visit (i.e., an age of 36 or younger at end of Year 7)

Primary analysis set Year 8 (PAS Year 8):

All women in the FAS with an age of 33 years or younger at baseline visit (i.e., an age of 36 or younger at end of Year 8)

The age at baseline (required for PAS Year 6, PAS Year 7 and PAS Year 8) will be used as recorded at baseline (Visit 2). If the age at baseline was not recorded, it will be calculated as the difference between year of baseline visit and year of birth recorded at screening visit.

Safety analysis set (SAF):

The SAF is identical with the FAS, i.e. all women who completed the baseline visit of the study.

6. Statistical Methodology

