6.1.3.1 Insertion procedure

The original indication for Mirena insertion (contraception, or contraception plus HMB) will be summarized descriptively.

The duration since Mirena insertion (at baseline visit) will be calculated as the difference between the Mirena insertion date and the baseline visit date.

For subjects with Mirena insertion on Feb 29th, 2012 or earlier, two leap years of 366 days will be considered between 2012 and 2017, i.e. duration since Mirena insertion will be calculated as:

$(\text{date of baseline visit} - \text{date of Mirena insertion}) / [(366 \times 2 + 365 \times 3) / 5]$.

For subjects with Mirena insertion after Feb 29th, 2012, one leap year of 366 days will be considered between 2012 and 2017, i.e. duration since Mirena insertion will be calculated as:

$(\text{date of baseline visit} - \text{date of Mirena insertion}) / [(366 \times 1 + 365 \times 4) / 5]$.

The duration of Mirena use since its insertion (at baseline visit) will be summarized descriptively as a continuous variable as well as a categorical variable:

- < 5 years minus 2 weeks
- 5 years minus 2 weeks, to 5 years
- > 5 years

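### For women with a late baseline visit, the Pearl Index denominator includes time before baseline in which a detected pregnancy could not have been counted; the bias is small, partial and always downward

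*SAP*

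**What the plan says.** - **Exposure rule.** For a baseline after Day 1 Year 6, SAP 6.2.1 states: "exposure and pregnancies between Day 1 Year 6 and baseline visit will be included". SAP Table 6-1 starts the 1-, 2- and 3-year clocks at Day 1 Year 6 whatever the baseline date, for example "Date of Mirena removal – Date of Day 1 Year 6 +1". Women who continue are credited a fixed 365 or 730 days, or up to 1095. Protocol Table 10-1 uses the same clock, but the protocol text has no sentence on a late baseline.
- **Who is analysed.** SAP 5.1 defines the full analysis set as "All women who completed the baseline visit of the study". Each primary analysis set is a subset of it.
- **Pregnancy found by baseline.** Protocol 9.6.3.4: "In case of a suspected pregnancy at screening or baseline visits, the subject must be withdrawn from the study and is considered a screening failure". SAP 4.2 likewise classes anyone who leaves before completing baseline as a screening failure.
- **Whether late baselines should occur.** Inclusion criterion 2 (Protocol 6.1) limits duration of use with the words "but not more than 5 years at visit 2", and Protocol 9.2 places baseline 14 to 0 days before the end of Year 5. A late baseline is therefore a deviation. The SAP still writes a rule for it and tabulates a category above 5 years in 6.1.3.1.
- **Partial conception dates.** SAP 4.3 imputes them to Day 1 Year 6.

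**The concern.** The SAP sentence looks symmetric, since it includes both exposure and pregnancies in the gap. The entry rules make it asymmetric. A woman is analysed only if she reached and passed a baseline visit with a pregnancy test, so her gap time was partly selected for the absence of the event being counted. This is survivor time, produced by starting the clock before the entry condition is met.

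The PI is the primary endpoint of an uncontrolled study, and the error can only make the product look better. The 1-year PI has the shortest denominator and is the primary result of the Year 6 analysis, which the protocol amendment links to a regulatory submission, so it is proportionally the most exposed.

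**Working it through.** **1. Can a gap pregnancy be counted?**

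| Conception in the gap | Enters the analysis sets? | Numerator | Gap in denominator |
|---|---|---|---|
| Detected at or before baseline | No, screening failure | Not counted | Not counted |
| Not yet detectable at baseline | Yes | Counted | Counted up to conception |
| No conception | Yes | None | Counted in full, unless removed for back-up use |

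The first row is the leak. Counted gap events can equal or fall short of true gap events but never exceed them, so the direction is fixed.

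**2. Reproducing the plan's figures (Protocol 10.4).** Inputs are 350 women and 15% dropout, read as per year with mid-year loss.
- Exposure: 350 × 0.925 × (1 + 0.85 + 0.85²) = 832.8 woman-years (WY); stated 832.
- First year alone: 350 × 0.925 = 323.75 WY (derived, not stated).
- Upper limit: 0.5 × χ²(0.975, 2(x+1)) / E. At E = 8.32 it is 0.868 for x = 2 and 1.054 for x = 3, so at most 2 pregnancies keep it at or below 1.
- Probability of at most 2 pregnancies: 76.7% at a true PI of 0.2 (stated 76%) and 54.5% at 0.3 (stated 55%).

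**3. Size of the gap.** WY at issue = 350 × share late × mean days late / 365. The documents give neither the share nor the delay, so both are assumed. The 3-year columns use 2 pregnancies and the 1-year columns use 1.

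| Share, delay | WY at issue | % of 832 | 3-year PI | 3-year upper limit | % of 323.75 | 1-year upper limit |
|---|---|---|---|---|---|---|
| SAP rule as written | – | – | 0.2404 | 0.8684 | – | 1.721 |
| 2%, 14 days | 0.27 | 0.03 | 0.2405 | 0.8686 | 0.08 | 1.722 |
| 10%, 30 days | 2.88 | 0.35 | 0.2412 | 0.8714 | 0.89 | 1.736 |
| 20%, 60 days | 11.5 | 1.4 | 0.2438 | 0.8805 | 3.6 | 1.784 |

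Each row removes the whole gap. Because early conceptions still count, these are upper bounds on the denominator effect for the assumed scenario.

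**4. Does the cut-off move?** With 2 pregnancies the upper limit passes 1 only if exposure falls below 722.5 WY. That means removing 832 − 722.5 = 109.5 WY, or about 114 days for each of 350 women (109.5 × 365 / 350). The cut-off of 2 does not change in any scenario above.

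**5. Pregnancies lost.** At a true PI of 0.2, 11.5 WY carries 0.002 × 11.5 = 0.023 expected pregnancies, so a loss is unlikely. One lost pregnancy would matter far more than the denominator, since the third moves the 3-year upper limit from 0.868 to 1.054.

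**The case against.** The strongest reply is that the gap is not event-free. A conception too recent to be detected at baseline enters both the analysis set and the numerator. If the delay is shorter than the test's detection lag, which the documents do not give, the rule excludes nothing and creates no bias. This stands: a reader might infer that the whole gap is immortal time, and the documents do not support that.

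A reader might also infer that the whole gap is always credited as unprotected, because the eDiary starts at baseline and missing back-up data count as no use. That goes too far as well. The first 28-day reference period starts at Day 1 Year 6, and any back-up use recorded in it removes the entire period, including its gap days. Back-up use confined to the gap does go unrecorded.

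It would likewise be tempting to say that the Kaplan-Meier failure rate has the same fault. SAP 6.2.1 states no time origin for it, so that holds only if its clock starts at Day 1 Year 6.

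Two partial safeguards exist. The Overall PI starts at baseline and so omits the gap, but it adds pre-Day 1 time for women with early baselines, so it does not correct the primary PI. Pregnancies in the screening period are reported and followed (Protocol 9.4.1.1), so a lost one would be on record, though not in the PI.

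Finally, changing the start date carelessly could do harm. Under the present imputation rule, a partial conception date in a late-baseline woman would be set to Day 1 Year 6, before the new start, and a pregnancy conceived after baseline could be dropped. This objection also stands, and the fix has to deal with it.

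**Conclusion.** The exposure rule for late baselines is biased in one direction on the primary endpoint, and no other rule corrects it. The bias is partial, being limited to the part of the gap in which a conception would have been detected by baseline, and it affects only women whose baseline visit was itself a deviation. Assuming 2-20% of 350 women are late by 14-60 days, at most 0.3-11.5 WY are involved. That is 0.03-1.4% of 832 WY for the 3-year PI and up to about 3.6% of the first-year exposure. The cut-off of 2 pregnancies is unchanged.

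A reader might infer that the rule could alter the trial's conclusion. The figures do not support that, and the plan sets no success threshold for the PI; the limit of 1 appears only in the sample size section. The case for changing the rule is its fixed direction and the modest cost of correction.

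**What to change.** 1. In SAP 6.2.1 and Table 6-1, and in Protocol Table 10-1 for consistency, start exposure for the 1-, 2- and 3-year PIs at the later of Day 1 Year 6 and the baseline visit. Shorten the 365-, 730- and 1095-day entries for continuing women by the same gap.
2. In SAP 4.3, impute partial conception dates to that same later date, so that no post-baseline pregnancy is lost.
3. State the Kaplan-Meier time origin. If it is Day 1 Year 6, use delayed entry at the later date.
4. List every pregnancy conceived on or after Day 1 Year 6 but before baseline, including those in screening failures, and show a sensitivity PI that counts them.
5. If the primary rule is kept, pre-specify the later-start calculation as a sensitivity analysis. In either case, report how many women had a late baseline and the length of the delays.

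The cost is slightly less exposure, several text edits that must agree with one another, and the possible move of a rare gap conception from the primary count to the sensitivity analysis. No new data are needed: the visit and insertion dates are recorded, and screening-failure pregnancies are already documented (Protocol 9.4.1.1 and 11.1).

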9.4.1.2 Pregnancies occurring after the end of study treatment

This section was changed in Amendment 1, see Sections 15.1.1.5 and 15.1.1.6.

All pregnancies detected up to 3 months after the removal of the Mirena must be reported to the sponsor; all subjects will be instructed to contact the investigator immediately if they

become pregnant less than 3 months after the removal of the Mirena. If the estimated date of conception is suspected to have occurred during study treatment (i.e. up to 7 days after EOT), further investigations will be conducted, and the pregnancy should be reported immediately and will be followed up according to the process described above for pregnancies during the study.

3-month follow-up contact: In addition, subjects who prematurely discontinued study treatment will be contacted unless the reason for discontinuation is “pregnancy”, “death”, or “withdrawal by subject” where the subject has withdrawn main consent during study conduct and wishes to stop future contact with the site. For subjects that had withdrawn consent during study, but consented to post study participation follow-up, post-treatment pregnancy tracking information is expected and they will be contacted by phone at 3 months after the removal of the Mirena. At this time, subjects will be asked if they have been pregnant after the study. If subjects could not be contacted at 3 months, they will be considered “Lost to Follow-up” for post-study pregnancy tracking.

12-month follow-up contact: Only subjects that prematurely discontinued treatment due to ‘Wish for pregnancy’ will be contacted and asked about pregnancies that occur within 1 year after end of treatment (EOT). If a subject was not pregnant at 3 month contact and no longer wishes to become pregnant, a 12-month contact is not required. If subject was “Lost to Follow-up” at 3 months, a 12-month contact is required.

PTPT information, i.e. data collected at the 3- and 12-month follow-up contacts, including information on all pregnancies identified, must be reported to the sponsor via electronic data collection tool (see Section 11.1). In addition, if the estimated date of conception is suspected to have occurred during study treatment, the pregnancy should be reported immediately according to the process described under section 9.4.1.1.

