A pregnancy will be allocated to the time period(s) that are relevant for the calculation of the PIs described above, e.g., a pregnancy that occurs on day 400 will be relevant for the 7th year PI, the two years PI (6th and 7th year), the three years PI (6th, 7th and 8th year), and the overall PI. Pregnancies that occur before Day 1 Year 6 of Mirena use will not count for the 1-year PI, 2-year PI and 3-year PI. Pregnancies that occur after the Mirena was removed or an expulsion was realized will not count for any PI.

It should be noted that e.g., pregnancies that occur after partial expulsion, but before Mirena removal will count for the PIs.

Furthermore, it should be noted that pregnancies that occur within 7 days after the end of exposure will count for the PIs.

Exposure times to be subtracted:

Subjects who apply additional concomitant contraception are not in risk or are under a lower risk of getting pregnant than subjects who do not apply additional contraception. In case a subject uses concomitant contraceptive methods (e.g., condoms to prevent STD); the respective 28-day reference period(s) of additional contraceptive method use will be excluded from the exposure time, unless a pregnancy occurred in that 28-day reference period.

Primary analysis

The primary method for the evaluation of the occurrence of pregnancy is the Pearl index defined as the number of pregnancies per 100 women years.

The PIs and the corresponding 2-sided 95 % confidence interval (CI) will be calculated using the model specified below.

Mathematical model for the calculation of the PI:

By assuming that the number of pregnancies follows a Poisson-distribution, the point estimate and the 95 % CI for the PI can be calculated as follows:

$$PI = x/E,$$

lower 95 % confidence limit of PI = $0.5 \times \chi^2_{(0.025, 2x)} / E$

upper 95 % confidence limit of PI = $0.5 \times \chi^2_{(0.975, 2(x+1))} / E$

where x = number of pregnancies,

E = exposure in 100 woman years (one woman year is 365 days of treatment exposure),

$\chi^2_{(\alpha, df)}$ is the alpha quantile from χ^2 -distribution with df degrees of freedom.

The primary analysis set will be the PAS Year 6 (for the analysis after 6 years), the PAS Year 7 (for the analysis after 7 years) and the PAS Year 8 (for the final analysis after 8 years), respectively. Furthermore, analyses will be repeated for the FAS.

Secondary analysis

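### SAP 6.2.1 and Protocol 10.3.2.1 exclude every pregnancy after removal or discovered expulsion, contradicting the 7-day counting rule that is meant to govern the Pearl Index

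*SAP*

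**What the plan says.** In SAP 6.2.1, the paragraph below Table 6–1 that allocates pregnancies to the PIs ends with the sentence "Pregnancies that occur after the Mirena was removed or an expulsion was discovered will not count for any PI calculation". The sentence that follows notes that "pregnancies that occur within 7 days after the end of exposure will count for the PI calculations". Nothing connects the two: there is no exception and no order of precedence.

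Protocol 10.3.2.1 has the same pair. It states "Pregnancies that occur after the Mirena was removed or an expulsion was realized will not count for any PI", and shortly afterwards "Furthermore, it should be noted that pregnancies that occur within 7 days after the end of exposure will count for the PIs".

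Table 6–1 fixes when exposure ends. For removal or partial expulsion, crude exposure in the 1-, 2- and 3-year PIs is "Date of Mirena removal – Date of Day 1 Year 6 +1". For total expulsion it is "Date, when expulsion was discovered – Date of Day 1 Year 6 +1".

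**The concern.** These sentences define the event for the primary variable. For a woman whose Mirena is removed or totally expelled, the end of exposure and the date of removal or discovery are the same day. The first 7 days after one are the first 7 days after the other, and the two sentences give opposite answers for a conception on those days.

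The window matters in practice. Every completer passes through removal. Protocol 7.4.1 and 8.2 warn that some removals carry a risk of pregnancy from intercourse in the preceding week. The home pregnancy test on the day of the 3-week contact will look for such pregnancies. Under the PI-specific imputation in SAP 4.3, a removal date with a missing day is set to the 15th. A known conception date from the 16th to the 22nd of that month would then be counted or not depending only on which sentence the programmer follows.

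Protocol 10.4 implies only about two pregnancies over years 6 to 8, so each one carries weight. The exclusion sentence can only lower the PI or leave it unchanged.

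**Working it through.** **1. The text.** Take a conception on day *d* after removal or discovered expulsion.

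| Day | Exclusion sentence | 7-day sentence |
|---|---|---|
| *d* = 1 to 7 | does not count | counts |
| *d* > 7 | does not count | silent |

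The conflict is confined to days 1 to 7.

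**2. Which rule is meant.** Three places point the same way.
- Protocol 9.4.1.2 calls for further investigation when conception is "suspected to have occurred during study treatment (i.e. up to 7 days after EOT", so on-treatment is taken to include those 7 days.
- SAP 6.2.1, describing the sensitivity analysis on complete 28-day cycles, begins "As for the primary analysis, pregnancies that occur within 7 days after the end of exposure as well as" and says that these count. It thus describes the primary analysis as using the 7-day rule.
- Protocol 15.1.1.5 gives the purpose of the 7-day wording as clarifying, at FDA request, how such pregnancies are counted for the PI.

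If the exclusion prevailed, the 7-day sentence would do nothing for removals and discovered expulsions, which are its obvious use.

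**3. The plan's own figures.** Inputs from Protocol 10.4: exposure 832 woman-years (E = 8.32 hundred) and a true PI of 0.2 or 0.3. From SAP 6.2.1: upper limit = 0.5 × χ²(0.975, 2(x+1)) / E.

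| x | PI = x/8.32 | Upper 95% limit |
|---|---|---|
| 0 | 0.000 | 0.443 |
| 1 | 0.120 | 0.670 |
| 2 | 0.240 | 0.868 |
| 3 | 0.361 | 1.054 |

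The upper limit stays at or below 1 for at most two pregnancies.
- True PI 0.2: mean 0.2 × 8.32 = 1.664, P(X ≤ 2) = 76.7% (plan: 76%).
- True PI 0.3: mean 0.3 × 8.32 = 2.496, P(X ≤ 2) = 54.5% (plan: 55%).

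Both reproduce.

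**4. Effect of one disputed conception.** Each pregnancy moves the 3-year PI by 1/8.32 = 0.12. Suppose exactly one conception falls on days 1 to 7, in addition to the Poisson count. If it is excluded, the probabilities are those above. If it is counted, the upper limit stays at or below 1 only when X ≤ 1: 50.5% at a true PI of 0.2 and 28.8% at 0.3. These figures are conditional on such a conception occurring.

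**5. Other exposures (assumptions).**
- The 832 woman-years are matched by 350 women losing 15% per year: 350, 297.5, 252.9 and 214.9 at the yearly marks, and 832.8 woman-years by the trapezoid rule.
- On that basis, years 6 and 7 together give about 599 woman-years. The upper limit is 0.930 with one pregnancy and 1.206 with two.
- Year 6 alone gives about 324 woman-years. Even zero pregnancies gives 1.139, so the comparison with 1 does not turn on this rule there.
- Two pregnancies keep the limit at or below 1 only with at least 722.5 woman-years. If back-up contraception removed 14% of exposure (716 woman-years), the critical step would move to one versus two.

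**6. Size of the window.** If all 350 women passed through it, it would hold 350 × 7/365 = 6.7 woman-years. The documents give no conception rate for the days after removal, so no probability is attached to the event in step 4.

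**The case against.** The strongest reply is that nobody who read the whole plan would be in doubt. The 7-day sentence follows the exclusion directly, in the form of a general rule and its exception, and step 2 confirms the intent. SAP 6.2.1 also requires a listing of every pregnancy with its conception date relative to the stop date of study drug administration, so any affected case would be visible. Most of this stands. A reader might infer that two competing analyses are open, and the documents do not support that. What remains is an exclusion with no exception in the current text of both documents. The listing would expose a disputed case without deciding it.

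Three stronger readings also fail.

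- *Double counting.* For women who continue, Table 6–1 caps exposure at 365 or 730 days, so a reader might infer that a conception on days 366 to 372 also enters the 1-year PI. SAP 6.2.1 defines that PI by pregnancies occurring during the sixth year, and its day-400 example allocates by date and omits the 1-year PI. The phrase about the end of exposure is loosely anchored, but no double count follows.
- *A pass/fail result hanging on one pregnancy.* Protocol 10.4 states that the sample size does not rest on statistical considerations, and no success criterion for the PI is given. The value of 1 describes precision.
- *Stale text in both documents.* In the Protocol, Amendment 1 added the 7-day sentence beside an exclusion already there. SAP v1.0 (05 Oct 2017) post-dates Amendment 1 (20 Sep 2017), so that history does not explain the SAP.

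**Conclusion.** The point holds as an error of wording in the primary-event rule. The exclusion sentence is wrong as written in both documents because it removes conceptions on days 1 to 7 after removal or discovered expulsion that the plan elsewhere means to count. Applied literally, it would understate the PI.

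Per affected pregnancy, the size is 0.12 on the 3-year PI at 832 woman-years. If it is the third pregnancy, the upper limit moves from 0.87 to 1.05, across the precision benchmark. This rests on the plan's expected exposure and its exact Poisson interval, and on such a conception occurring at all. No formal conclusion in the plan depends on it. It is worth correcting because events are few and the correction is simple.

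**What to change.** In SAP 6.2.1 and Protocol 10.3.2.1, replace the two sentences with one rule:

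> Pregnancies with an estimated conception date more than 7 days after Mirena removal or discovery of expulsion do not count for any PI; those conceived up to and including day 7 count.

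Add four clarifications:
- The 7 days run from removal or discovered expulsion. The conception of a woman who continues past day 365 or 730 is allocated by its date only, as the definitions and the day-400 example already imply.
- Where no removal or expulsion date exists, the date Mirena was last known in situ serves as the anchor, in line with SAP 4.3.
- The Kaplan-Meier analysis uses the same event rule. SAP 6.2.1 at present gives it no event or censoring rule for these cases.
- State whether the pregnancy row or the removal row of Table 6–1 sets exposure when conception follows removal. The difference is at most 7 days per case and is negligible.

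The cost is wording in two documents. Sample size, exposure and data collection do not change.
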